## Statistical Analysis Plan

Sponsor Name: Nitto Denko Corporation  
Sponsor Protocol ID: ND-L02-s0201-005

### 7.5.5.2 Other analyses

Analyses to compare treatment effect between the two active treatment arms may be conducted ad hoc if both low dose and high dose treatment arm shows significant results versus the placebo arm.

## 7.6 Safety

### 7.6.1 Extent of Exposure

Duration of exposure will be summarized descriptively as a continuous variable in days, and also in the following categories:

- 0 - <2 weeks (14 days);
- 2 - <4 weeks (28 days);
- 4 - <6 weeks (42 days);
- ...;
- 20 - ≤23 weeks (161 days)

The number and percent of subjects who received the premedication will be summarized by visit and overall and treatment arm. The volume and dosage for study treatment infusion will be summarized descriptively by visit or overall and treatment arm.

The number and percent of subjects who have at least 1 infusion interruption, and number and percent of subject who have at least 1 infusion interruption not resumed at any visit as documented in the eCRF will be summarized by visit or overall and treatment arm.

The number of infusion interruptions per subject will be summarized both as a continuous variable using descriptive statistics, and as a categorical variable (categories: 0, 1, and ≥2) by visit or overall and treatment arm. Reasons for the infusion interruptions will also be presented. A reason that was recorded multiple times at different visits for one subject will be counted once for this subject for overall summary. In addition, the number of subjects who have at least 1 infusion interruption resumed at any visit, and the duration of such interruptions will be summarized. A listing will be provided for subjects with any infusion interruptions.

## Statistical Analysis Plan

Sponsor Name: Nitto Denko Corporation  
Sponsor Protocol ID: ND-L02-s0201-005

Treatment compliance will be summarized descriptively by treatment arm for the SAF population. The following percentage compliance categories will also be summarized:

- <60%
- 60 – 79%
- 80 – 100%
- >100%

Subjects who missed 1 or 2 doses of study treatment due to COVID-19 pandemic as permitted by protocol will be summarized separately for exposure duration, total number of doses, and treatment compliance. A swimmer plot will be created for all scheduled study treatment administration from Day 1 to end of study. Events of IP administration, skipping study treatment due to COVID-19 pandemic, or treatment termination will be included.

### 7.6.2 Adverse Events

All AE data will be listed. Treatment-emergence status will be flagged in the listing. In addition, corresponding listings of serious AEs (SAEs), AEs resulting in death, TEAEs leading to discontinuation of study treatment, and TEAEs of special interests will be produced.

An overview table will summarize the number of all TEAEs, the number and percentage of subjects with at least one of the following TEAEs, by standard of care (none, nintedanib, pirfenidone), treatment arm and overall, where subjects with more than one TEAE in a particular category are counted only once in that category:

- any TEAE;
- any TEAE by relationship (definite, probable, possible, unlikely, none);
- drug-related TEAE;
- any TEAE by severity (mild, moderate, severe, life-threatening consequences, death);
- TEAE leading to study treatment interrupted;
- TEAE leading to study treatment withdrawn;
- TEAE leading to discontinuation from the study;
- Treatment-emergent SAEs;
- drug-related SAE;
- AEOIs
- Each AEOIs
  - [REDACTED]
  - [REDACTED]
    - Respiratory adverse events
    - Acute exacerbation of idiopathic pulmonary fibrosis
- TEAE leading to death;

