### **14.2. Adverse Event Classification**

#### **14.2.1. Treatment-Emergent Adverse Events**

An AE is defined as treatment-emergent if it occurs at or after the first dose of study treatment and through 2 weeks after the last dose of study treatment. This also includes AEs which are observed before the first dose of study treatment and increase in severity after the first dose through 2 weeks after the last dose of study treatment.

Note: 2 weeks after the last dose of study treatment was selected because it is expected to be longer than 5 times the terminal half-life of ND-L02-s0201.

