## 3. Efficacy and Safety Variables

### 3.1 Primary Endpoints

#### Safety

- Incidence of TEAEs and treatment-emergent SAEs
- Proportion of subjects discontinuing study treatment due to TEAEs

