### 3.4.6 Adverse Events (AEs)

All AEs recorded on the eCRF will be coded using the latest version of MedDRA dictionary, per the Data Management Plan, throughout the study and classified as either pre-treatment AEs or TEAEs as follows:

- Pre-treatment AEs are events that started prior to the first dose of any study treatment, including pre-medication.
- TEAEs are events that occur on or after the first dose of any study treatment including pre-medication through two weeks after the last dose of study treatment or adverse events which start before the first dose of study treatment, but increase in severity after the first dose through two weeks after the last dose of study treatment.

Assessment of AE severity will be based on the National Cancer Institute (NCI) Common Terminology Criteria for Adverse Events version 5.0 (CTCAE v5.0). The severity of all AEs is recorded as mild (Grade 1), moderate (Grade 2), severe (Grade 3), life threatening consequences (Grade 4), or death (Grade 5), per CTCAE grading. If severity is missing for a TEAE, it will be considered severe only in the overall category in the summary tables.

The relationship between an AE and study treatment is assessed as definite, probable, possible, unlikely, or none. A drug-related AE is an AE considered by the investigator as definitely, probably, possibly, or unlikely related to study treatment. If the relationship is unknown or missing, it is also considered as related to study treatment.

AEs of special interest (AEOI) include [REDACTED] respiratory adverse events, and acute exacerbation of idiopathic pulmonary fibrosis.

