## Statistical Analysis Plan

Sponsor Name: Nitto Denko Corporation  
Sponsor Protocol ID: ND-L02-s0201-005

the corresponding times have not been recorded. Measurements that are obtained after the first date of study treatment will be considered post-baseline values. Change from baseline is defined as (post-baseline value – baseline value).

Time-to-event endpoints will be summarized using Kaplan-Meier (KM) method to estimate the median, and the 25th and 75th percentiles.

The following principles will be applied to all TFLs unless otherwise stated:

Principle	Value
Treatment arm labels and order presented	1. Placebo 2. ND-L02-s0201 45 mg 3. ND-L02-s0201 90 mg 4. Total (if applicable)
Tables	Data in summary tables for safety will be presented by treatment arm, and Total, and visit (where applicable). Data in summary tables for efficacy will be presented by treatment arm.
Listings	All data collected presented by treatment arm, subject, and visit date (where applicable), unless otherwise specified.
Descriptive summary statistics for continuous variables	Number of subjects (n), mean, standard deviation, median, minimum, maximum
Descriptive summary statistics for categorical variables	Frequency counts and percentages [n (%)]
Denominator for percentages	By-visit summaries: number of subjects with non-missing data at the visit assessed in the analysis population of each treatment arm; Other summaries: Number of subjects in the analysis population of each treatment arm, unless specified otherwise.
Include "Missing" as category	Included for demographics and other baseline characteristics when the number of missing is greater than zero for at least one treatment arm. Missing post-baseline values will not be summarized, unless otherwise specified.
Display for percentage	One decimal place, except for 100%
Display for 0 percentages	blank
Display to one more decimal place than collected value	Mean, Median

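### TEAE and treatment-emergent SAE incidence is planned only as crude percentages, so with unequal stopping between arms, events due after stopping are under-counted in the arm with shorter exposure

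*SAP*

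**What the plan says.** The primary endpoints (SAP 3.1; Protocol 13.1.1) are "Incidence of TEAEs and treatment-emergent SAEs" and "Proportion of subjects discontinuing study treatment due to TEAEs". No time unit is attached to either.

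The counting window is tied to each subject's own last dose. SAP 3.4.6 counts events "on or after the first dose of any study treatment including pre-medication through two weeks after the last dose of study treatment", and Protocol 14.2.1 sets the same two-week limit. The protocol gives its reason: "it is expected to be longer than 5 times the terminal half-life of ND-L02-s0201".

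The overview table in SAP 7.6.2 reports the number of TEAEs and "the number and percentage of subjects with at least one of the following TEAEs". The tables by system organ class and preferred term, and the serious-TEAE and AEOI tables, also give number and percentage of subjects. For summaries that are not by visit, the general rule in SAP 7.1 sets the denominator: "Other summaries: Number of subjects in the analysis population of each treatment arm, unless specified otherwise".

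For acute exacerbation, respiratory hospitalisation, death and transplantation, SAP 7.5.2.4 and 7.5.2.5 define rates per 100 patient-years and add time-to-event analyses. The readable text of 7.6.2 has neither for TEAEs. Two bullets after the AEOI summaries are blacked out, so the absence is established for the readable text only.

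**The concern.** A subject who stops after one infusion counts in the denominator exactly like one who receives all twelve, but can contribute treatment-emergent events for only a fraction of the time. When stopping is similar across arms this matters little. When it differs, the percentages no longer compare like with like.

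The second primary endpoint is discontinuation because of TEAEs, so the trial sets out to measure one source of unequal stopping. If that occurs, the figures for the other primary endpoint lose comparability for events that had not yet happened at stopping. The SAP plans no between-arm test of adverse events, so readers will judge safety by comparing these percentages by eye.

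**Working it through.** **The plan's own day count.** Dosing is every 2 weeks for 12 doses (Protocol Table 1), so dose k falls on Day 1 + 14(k − 1). Dose 12 is Day 155, and 155 + 14 = Day 169, the stated end-of-treatment day. Time at risk after k doses is therefore 14k days:

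- 1 dose: 14 days (8% of the full window)
- 3 doses: 42 days (25%)
- 6 doses: 84 days (50%)
- 12 doses: 168 days (100%)

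**Assumed inputs.** The documents give no event risks or stopping rates. For illustration: the same constant hazard h in both arms; 20% risk over 168 days; 10% stopping in one arm and 30% in the other; stopping unrelated to the event being counted.

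**Formulas.** h = −ln(0.80)/168 = 0.001328 per day. The event risk after k doses is 1 − exp(−14kh) = 1 − 0.80^(k/12). With a fraction d stopping, crude incidence = (1 − d) × 0.20 + d × (mean risk among stoppers).

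**Stops spread evenly over doses 1 to 11.** Mean risk among stoppers is 0.104.
- d = 0.10: 0.180 + 0.0104 = 19.0%
- d = 0.30: 0.140 + 0.0312 = 17.1%
- Gap 1.9 points (7.6 versus 6.8 subjects in 40)

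**All stops after doses 1 to 3.** Mean risk among stoppers is 0.0364.
- d = 0.10: 0.180 + 0.0036 = 18.4%
- d = 0.30: 0.140 + 0.0109 = 15.1%
- Gap 3.3 points (7.3 versus 6.0 subjects in 40)

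**With time at risk in the denominator.** The rate is h × 365.25 × 100 = 48.5 per 100 patient-years in both arms, so the gap disappears.

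**Range.** With 10–30% event risk and 20–40% stopping against 10%, the spurious gap is 0.5 to 4.2 points (even stops) or 0.9 to 7.3 points (early stops). A true hazard ratio of about 1.06–1.21 (even) or 1.10–1.45 (early) could then show as equal percentages. A larger excess still shows: at hazard ratio 1.5 with 20% risk and 10% versus 30% stopping, the crude figures are 19.0% versus 24.4% (even) or 18.4% versus 21.5% (early).

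**When a TEAE causes the stop.** Such a subject is already an any-TEAE case. Assume a 30% risk over 24 weeks, 10% versus 25% stopping, and an 8-week window for stoppers.
- No stop caused by a TEAE: stoppers have risk 1 − 0.70^(8/24) = 11.2%. Crude incidence is 0.90 × 0.30 + 0.10 × 0.112 = 28.1% versus 0.75 × 0.30 + 0.25 × 0.112 = 25.3%.
- Every stop caused by a TEAE: 0.90 × 0.30 + 0.10 = 37.0% versus 0.75 × 0.30 + 0.25 = 47.5%. The arm that stops more looks worse.
- Break-even: if a share f of stops is TEAE-driven, stoppers' incidence is f + (1 − f) × 0.112. This equals 0.30 at f = 0.188/0.888 = 0.21. At f = 0.20 the arms show 29.9% versus 29.7%.

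For a common event the result is similar: with 80% risk in non-stoppers and all stops TEAE-driven, 10% stopping gives 0.90 × 0.80 + 0.10 = 82%, and 30% gives 0.70 × 0.80 + 0.30 = 86%.

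**The case against.** A reader might infer that the plan makes a poorly tolerated drug look safer on the trial's primary question. The documents do not support that, for three reasons. A TEAE-driven stopper is counted in any-TEAE incidence with certainty, and under the assumptions shown the spurious gap is gone once about one fifth of stops are TEAE-driven. The second primary endpoint rises when an arm is poorly tolerated and is reported beside the first. And nothing in either document says an active arm will stop more often; if placebo stops more, the distortion runs the other way.

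A reader might also infer that the two-week window is wrong. It has a stated half-life rationale, and this point does not challenge it.

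The plan also has partial safeguards. Exposure duration is tabulated by category and a swimmer plot shows treatment termination (SAP 7.6.1). TEAEs leading to withdrawal are tabulated. Adverse events are collected for 12 weeks after the last dose (Protocol 14.5) and listed with a treatment-emergence flag. Several of the gravest outcomes already have patient-year rates and time-to-event analyses. With no test attached, a gap of about one subject in 40 is small beside sampling noise: 40 per arm would have 80% power at two-sided 0.05 only for something like 20% versus 49%.

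All of this stands, and it limits the size and direction of the point. It does not remove it: the exposure tables show that time at risk differs but leave the percentages unadjusted, and no readable table counts the events after the window closes.

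**Conclusion.** The point holds in a limited form. In the readable SAP, TEAE and treatment-emergent SAE incidence is given only as crude percentages, while time at risk can differ twelvefold between subjects (14 to 168 days). With unequal stopping, this understates later events in the arm with shorter exposure, whichever arm that is. The measures affected are treatment-emergent SAEs, AEOIs and individual preferred terms other than the event that caused stopping. No general direction can be claimed for any-TEAE incidence.

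The central illustration gives a spurious gap of about 2 to 3 percentage points. It rests on a constant hazard equal in both arms, a 20% risk, 10% versus 30% stopping, and stopping unrelated to the event; all of these are assumptions. This is a worthwhile, inexpensive improvement to the safety tables, not a flaw that invalidates them.

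**What to change.** Keep n (%) in SAP 7.6.2. For any TEAE, treatment-emergent SAEs and AEOIs, add one of the following by arm, with 95% CIs and labelled descriptive:

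- subjects with a first event per 100 patient-years at risk, with time running from first dose to the earlier of first event and last dose + 14 days; or
- cumulative incidence at Week 24, censored at the end of the TEAE window.

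By-arm estimates without a between-arm test stay consistent with the SAP's decision not to compare adverse events formally.

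The cost is SAP wording and slightly more tabulation. The adverse event and dosing dates needed are already collected. The rate version assumes a roughly constant hazard, which infusion-related reactions may not follow; the cumulative-incidence version avoids that assumption. Both still treat stopping as uninformative about the event being counted, which a footnote should say.

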## Statistical Analysis Plan

Sponsor Name: Nitto Denko Corporation  
Sponsor Protocol ID: ND-L02-s0201-005

This summary table will be repeated for each of the following COVID-19 vaccination status:

- Subjects vaccinated prior to start of study treatment
- Subjects vaccinated while on treatment
- Subjects not vaccinated

The number and percentage of subjects reporting each TEAE will be summarized by System Organ Class (SOC) and Preferred Term (PT) by treatment arm and overall for the SAF population. Tables will be sorted alphabetically by SOC. PTs will be sorted by descending overall total. The following summaries will be produced:

- TEAEs, by SOC and PT;
- TEAEs by PT; this table will also be repeated for each COVID-19 vaccination status as described above;
- TEAEs with frequency >10% in one or more treatment arms by PT;
- TEAEs related to the study treatment, by SOC and PT;
- TEAEs related to the study treatment, by PT;
- TEAEs by relationship to the study treatment, by SOC and PT;
- TEAEs related to pre-medication, by SOC and PT;
- TEAEs by maximum severity and PT;
- TEAEs related to the study treatment by maximum severity and PT;
- TEAEs leading to the study treatment interruption, by SOC and PT;
- TEAEs leading to the study treatment withdrawn, by SOC and PT;
- TEAEs related to the study treatment leading to the study treatment withdrawn, by SOC and PT;
- Serious TEAEs, by SOC and PT;
- Serious TEAEs related to the study treatment, by SOC and PT;
- Serious TEAEs with frequency >5% in one or more treatment arm by PT;

In the above summaries, subjects with more than one AE within a particular SOC are counted only once for that SOC. Similarly, subjects with more than one AE within a particular PT are counted only once for that PT. For summaries by maximum severity, subjects with multiple AEs within a particular SOC or PT will be counted under the category of their most severe AE within that SOC or PT. AEs with missing severity will be included as severe in the overall count of subjects with AEs, but will not be included in the counts of subjects with AEs within a SOC or PT.

The number and percentage of subjects with at least 1 treatment-emergent AEOI, and each type of treatment-emergent AEOI will be summarized. The number and percentage of subjects reporting at least 1 treatment-emergent AEOI will be summarized by SOC and PT for the following in the SAF population:

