## Statistical Analysis Plan

Sponsor Name: Nitto Denko Corporation  
Sponsor Protocol ID: ND-L02-s0201-005

- If the year and month of the AE start date is the same as the year and month of the first dosing date, the day will be imputed using the day of first dosing date;
- Otherwise, the day will be imputed as the first day of the month.
- If an imputed AE start date is later than the corresponding AE end date, the imputed AE start date will be replaced with the AE end date.

AEs with missing relationship (related or not related) to study treatment will be treated as related AEs in summaries of AEs by relationship to study treatment.

Partial dates with day or day and month missing for concomitant medications date will be imputed as follows:

- If the year and month are present and the day is missing, set the start date as the first day of the month, and set the end date as the last day of the month as applicable.
- If the year and day are present and the month is missing, set the month to January as the start date, and set month to December as the end month as applicable.
- If the year is present and the month and day are missing, set January 1 as the start date, and set December 31 as the end date as applicable.
- Completely missing dates will not be imputed.
- If the start date is completely missing and the end date is on or after the first dosing date, the medication will be classified as concomitant; if the end date is missing, the medication will be classified as ongoing. Medications for which both the start and end dates are missing will be classified as concomitant.

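### TEAEs with missing severity count as severe overall but are left out of their own SOC and PT counts: the two maximum-severity tables undercount, and the rule's reach into other tables is unclear

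*SAP*

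**What the plan says.** The rule for missing severity appears twice in the SAP.

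- Section 3.4.6 (Adverse Events) gives it as a grading rule: "If severity is missing for a TEAE, it will be considered severe only in the overall category in the summary tables".
- Section 7.6.2 (Adverse Events), in the paragraph after the list of TEAE tables, adds an exclusion. Such events enter the overall count as severe, "but will not be included in the counts of subjects with AEs within a SOC or PT".

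The surrounding text in 7.6.2 bears on how far that exclusion reaches. The paragraph opens with a rule for the whole list: "In the above summaries, subjects with more than one AE within a particular SOC are counted only once for that SOC". The sentence immediately before the exclusion is narrower: "For summaries by maximum severity, subjects with multiple AEs within a particular SOC or PT will be counted under the category of their most severe" event. The general tables are introduced with no condition on severity: "The number and percentage of subjects reporting each TEAE will be summarized by System Organ Class (SOC) and Preferred Term (PT) by treatment arm".

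Other missing AE attributes are handled without removing the event. Under SAP 6.2, "AEs with missing relationship (related or not related) to study treatment will be treated as related AEs", and a completely missing start date makes the event treatment-emergent.

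**The concern.** When the severity field is blank, the subject, the coded term and the fact that the event occurred are still known. A missing grade is a reason to be careful about the severity column. It is not a reason to drop the subject from the row for that term. Missing severity is also the exception within the SAP: for missing relationship and missing start date the event is kept and classified conservatively.

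The incidence of TEAEs and treatment-emergent SAEs is the primary endpoint (SAP 3.1), and no statistical comparison of AEs between arms is planned (SAP 7.6.2). Safety will therefore be read from descriptive counts with about 40 subjects per arm, and the SOC and PT rows show which kind of event occurred. A rule that lowers some of those counts, with a scope that two programmers could reasonably read differently, should be settled before the tables are produced.

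**Working it through.** The documents give no figure for this rule, so there is nothing to reproduce. The check compares the text and then sizes the effect.

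**1. Scope of the exclusion.** Two readings are open.

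- *Contextual reading.* The sentence completes the maximum-severity rule that it follows. It then applies to two of the 15 listed tables: "TEAEs by maximum severity and PT", and the same table restricted to events related to study treatment.
- *Literal reading.* The sentence has no limit of its own, refers to counts of subjects with AEs and not to counts by severity, and stands in a paragraph that opens by referring to all the listed summaries. It then also applies to the general, related and serious SOC/PT tables.

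**2. Consequence on either reading.** Take the maximum-severity table by PT.

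- Subject X has one event in a PT, ungraded, and no other event graded severe or worse. X is severe in the overall row but absent from that PT row, so no PT row shows the event that made X severe overall. On the contextual reading X is still counted for that PT in the TEAEs-by-PT table, so the two tables give different subject counts for the same term.
- Subject Y has one mild and one ungraded event in the same PT and nothing graded higher elsewhere. Y is mild in the PT row and severe in the overall row.

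**3. Consequence on the literal reading only.** Inputs: n = 40 per arm (SAP 2.3, approximate), and cut-offs of >10% for TEAEs and >5% for serious TEAEs (SAP 7.6.2).

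| Table | Smallest count above cut-off | After losing one subject | Still above? |
|---|---|---|---|
| TEAEs >10% | 5/40 = 12.5% | 4/40 = 10.0% | No |
| Serious TEAEs >5% | 3/40 = 7.5% | 2/40 = 5.0% | No |

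Three conditions must all hold for a PT to leave its table: the subject's events in that PT are all ungraded, the arm sits exactly at the minimum count, and no other arm exceeds the cut-off.

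**4. How often a subject would be lost.** The documents give no rate of missing grades, so the rate m is an assumption. With k subjects who each have a single event in the PT, and independence, the chance that at least one is ungraded is 1 − (1 − m)^k.

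| Assumed m | k = 5 | k = 3 |
|---|---|---|
| 0.5% | 2.5% | 1.5% |
| 1% | 4.9% | 3.0% |
| 2% | 9.6% | 5.9% |
| 5% | 22.6% | 14.3% |

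For example, at m = 1% and k = 5: 1 − 0.99^5 = 0.049. These are chances of losing at least one subject from a given PT. The chance that the PT then drops out of its table is smaller, because the no-other-arm condition must also hold.

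**The case against.** The best defence is that the sentence belongs to the maximum-severity rule before it. Section 3.4.6 supports this: it assigns a grade and removes nothing from incidence. The general SOC/PT tables are defined with no severity condition. On this reading those tables, the serious tables and both frequency cut-off tables are complete, and neither row of the 40-per-arm illustration applies.

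The consequences are also limited. Protocol 14.2.8 requires AEs to be graded and supplies definitions for terms that CTCAE does not list, so few grades should be missing. The subject stays in the overall count, classified conservatively as severe. SAP 7.6.2 lists all AE data, with separate listings for serious events, deaths, discontinuations and events of special interest, so the term remains visible and any gap can be traced.

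Most of this stands. A reader might infer that toxicities vanish from the tables showing what occurred, or that the primary endpoint is undercounted. The documents do not support either as a settled fact: the first needs the literal reading, and the overall TEAE count keeps the subject even then. What the defence does not remove is the undercount in the two maximum-severity tables, which occurs on every reading, or the lack of an explicit limit on the exclusion.

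**Conclusion.** The point holds in limited form. As written, the two maximum-severity tables by PT undercount any term in which a subject has only ungraded events, and their PT rows do not match the overall severe count. The reach of the exclusion into the general, related and serious SOC/PT tables is ambiguous. Only if the sentence is applied literally can one lost subject take a term below the >10% or >5% cut-off, under the three conditions above and with n = 40 assumed.

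The likely number of affected subjects is small, but the documents give no rate from which to calculate it. The 0.5% to 5% range is purely illustrative. No planned AE test is affected, because none is planned. The change is still worth making: a stated counting rule gives a wrong count for a known event, and the correction is cheap.

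**What to change.** Replace the exclusion sentence in SAP 7.6.2 with wording such as:

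> Every TEAE is counted in its SOC and PT in all incidence tables regardless of grade. In maximum-severity tables, subjects whose only events in a PT are ungraded are shown in a Missing category.

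Amend 3.4.6 to agree, making clear that treating a missing grade as severe in the overall category assigns a grade there and does not remove the event from its SOC or PT. The Missing category must be stated explicitly, because the default in SAP 7.1 is not to summarize missing post-baseline values.

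Counting such subjects as severe within the PT would also restore the counts, but it attaches an unobserved grade to a specific toxicity; a Missing category avoids that. A footnote can cover the remaining case of a subject with graded and ungraded events in the same PT, who appears under the recorded grade in that row and as severe overall. The cost is a sentence or two in the SAP and one extra table column.
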